2.4.1 Study treatment

The number of study doses administered, duration on study, duration of exposure, patient year of exposure will be summarized by treatment group and Part. The analysis of exposure will also be provided for overall i.e., Part 1 and 2 data combined. Listings will be provided.

The number of participants dosed, and the injection site location will also be summarized by study visit and treatment group.

Duration of exposure will be calculated as: minimum of (Date of last dose of treatment – Date of first dose of treatment + 180 + 1, Date of last known visit – Date of first dose of treatment + 1). For Part 1 data analysis, duration of exposure will be truncated at data cut-off date.

Patient-year of exposure will be calculated as duration of exposure/365.25.

Duration on study is defined as: date of last known visit on study – date of first dose of treatment + 1. For Part 1 data analysis, duration on study will be truncated at data cut-off date.

The patients who will discontinue the treatment prematurely before discontinuing the treatment period will be summarized by treatment group and Part, including the reason of treatment discontinuation. Listing will also be provided.

2.4.2 Prior and concomitant therapies

Prior (pre-baseline) therapies are defined as any medication that was stopped ≥ 1 day before the first dose date of study medication. They will be summarized by treatment group.

Concomitant therapies (any medication given at least once between the day of first dose of randomized study treatment and the date of the last study visit, including those which were started pre-baseline and continued into the period when study treatment is administered) will be summarized by treatment group and Part. Listings will be provided.

Lipid-modifying therapy (LMT) use, will be summarized separately at screening and at the baseline/Randomization visit (Day 1) by treatment group using the following categories:

• Any LMT

Novartis SAP amendment 4	For business use only	Page 23 CKJX839C12301
• No LMT		
• Statins		
• Statins only		
• Other LMT		
• Other LMT only		
• Ezetimibe		
• Ezetimibe only		

New or changed lipid-modifying therapy, summarized by treatment group and Part.

Significant non-drug therapies prior to and after the start of the study treatment will be summarized according to the Anatomical Therapeutic Chemical (ATC) classification system and preferred term, by treatment group and Part. Significant non-drug therapies will be summarized similarly by primary system organ class, preferred term, treatment group and Part.

2.5 Analysis of the primary objective

The primary objective is to demonstrate superiority of inclisiran compared to placebo in reducing LDL-C [percent change] at Day 330 (Year 1) in adolescents (aged 12 to <18 years) with HeFH and elevated LDL-C.

2.5.1 Primary endpoint

The primary endpoint, i.e., primary analysis variable, is the percentage change in LDL-C from the baseline measurement to the Day 330 visit.

The primary clinical question of interest is: What is the effect of the test treatment versus placebo on change in LDL-C after 330 days of treatment in adolescents with HeFH and elevated LDL-C who are on stable, optimal standard of care (SoC) lipid-lowering therapy, regardless of treatment discontinuation for any reason and regardless of unforeseen change in the concomitant lipid-lowering therapy.

The justification for the primary estimand is that it will capture both the effect of the study drug and the effect of changes in additional medication(s) used for HeFH, if they occur, as would be the case in clinical practice.

The primary estimand is described by the following attributes:

- 1. **Population**: Adolescents with the HeFH condition of interest and elevated LDL-C on stable optimal SoC lipid-lowering therapy. Further details about the population are provided in Section 5 of the study protocol.
- 2. Endpoint: Percentage change in LDL-C from baseline to Day 330 (Year 1)
- 3. **Treatment of interest**: The randomized treatment (the investigational treatment inclisiran or the control treatment placebo) as add-on to optimal SoC lipid-lowering therapy for HeFH.

Novartis	Confidential	Page 25 of 48
Clinical Study Report Appendix 16.1.9, v1.0		Study No. CKJX839C12301

Novartis	For business use only	Page 24
SAP amendment 4		CKJX839C12301

The type and dose of the concomitant lipid-lowering therapy for HeFH must remain stable during Part 1 (Year 1) of the study. Further details about the investigational treatment and control treatment are provided in Section 6 of the study protocol. Data collected regardless of treatment discontinuation for any reason, regardless of unforeseen change in the concomitant lipid-lowering therapy will be used for analysis [Treatment policy].

4. **The summary measure**: difference between treatments in mean percentage change from baseline to Day 330.

2.5.2 Statistical hypothesis, model, and method of analysis

The statistical hypotheses that will be tested are as follows:

- H0: The difference between inclisiran and placebo in the least squares mean percentage change from baseline to the Day 330 visit in LDL-C= 0
- Ha: The difference (inclisiran minus placebo) between participants treated with inclisiran and placebo in the least squares mean percentage change from baseline to the Day 330 visit in LDL-C < 0

The primary objective will be achieved if the null hypothesis is rejected at significance level of 0.025 (One-sided test).

The primary analysis will use an analysis of covariance (ANCOVA) model. Due to probable heterogeneity of variances between treatment groups, ANCOVA model which assumes unequal variances for treatment group will be used. The model will include the fixed effects of treatment group and baseline age group (≥ 12 -<15 or ≥ 15 -<18 years of age), with baseline LDL-C as a covariate. Multiple imputation will be used to impute missing data using a washout model specified in Section 5.7.1. A total of 100 imputed datasets will be created. The ANCOVA model will be fit to each imputed dataset, and results will be combined using Rubin's combination rules. The estimate and corresponding 2-sided 95% confidence intervals of mean difference between treatment groups will be calculated. P-value for hypothesis test for mean difference will also be provided. The FAS will be used for this analysis.

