- **Part 2 (Year 2):** 12 months single arm, open-label follow-up period with all participants receiving inclisiran sodium 300 mg (equivalent to 284 mg inclisiran^{*}) s.c. Participants randomized to placebo in Part 1 will receive inclisiran starting on Day 360 ("Switch" Day 360). Participants randomized to inclisiran in Part 1 will receive placebo on Day 360. This dose of inclisiran/placebo on Day 360 will remain blinded in order to maintain the blind for Part 1 of the study. All participants will receive subsequent doses of open-label inclisiran on Days 450 and 630.
- * Inclisiran is also referred to as KJX839.

[figure not shown]
Informed consent will be obtained before initiation of any study-specific procedures (see Section 5.1 and Section 7 for details). Participants who meet the inclusion/exclusion criteria will be required to maintain their current lipid-lowering treatment unchanged for Part 1 (Year 1) of the study (including the screening/run-in period). Investigators must ensure that each participant receives individualized, optimal SoC lipid-modifying treatment [including maximally tolerated statin treatment (investigator's discretion) with or without other lipid-lowering therapy (e.g. ezetimibe)], and that this treatment was stable for \geq 30 days before screening. Maximum tolerated dose of statin is defined as the maximum dose of statin that, at the investigator's discretion, can be taken on a regular basis without AEs that would lead to a reduction in statin dose. Intolerance to statin must be documented and enrollment of statin-intolerant participants will be capped at approximately 15%.

A minimum of 102 participants (actual expected number of participants: approximately 130) who meet the inclusion/exclusion criteria will be randomized in a 2:1 ratio to receive either inclisiran sodium 300 mg s.c. or placebo on Day 1 (baseline). Randomization will be stratified by age (\geq 12 to <15 years and \geq 15 to <18 years to include a minimum of 40 participants in each of the two age strata). A second and third dose of inclisiran or placebo will be given on Day 90 and Day 270, respectively. The primary endpoint will be measured at Day 330.

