5.1 Inclusion criteria

Participants eligible for inclusion in this study must meet **all** of the following criteria:

- 1. Written informed consent must be obtained from the participant's parent(s)/legal representative(s) prior to the adolescent's participation in the study. A consent or assent may also be required for some participants depending on their age and local requirements. *An informed consent must be obtained from participants once they reach the local legal age of adulthood during the study.*
- 2. Male or female participants, ≥ 12 to < 18 years of age at screening
- 3. HeFH diagnosed either by genetic testing or on phenotypic criteria according to the European Atherosclerosis Society Consensus Panel (i.e. elevated LDL-C plus a family history of elevated LDL-C, premature coronary artery disease and/or genetic diagnosis); see Section 16.1 (Appendix 1) for details of the criteria including LDL-C cutoffs
- 4. Fasting LDL-C >130 mg/dL (3.4 mmol/L) at the screening visit, measured at the central laboratory
- 5. Fasting triglycerides <400 mg/dL (4.5 mmol/L) at the screening visit, measured at the central laboratory
- 6. On maximally tolerated dose of statin (investigator's discretion) with or without other lipidlowering therapy (e.g. ezetimibe). Maximum tolerated dose of statin is defined as the maximum dose of statin that, at the investigator's discretion, can be taken on a regular basis without AEs that would lead to a reduction in statin dose
- 7. Participants on lipid-lowering therapies (such as statin and/or e.g. ezetimibe) should be on a stable dose for \geq 30 days before screening with no planned medication or dose changes during study participation
- 8. Participants on a documented regimen of LDL-apheresis will be allowed to continue the apheresis during the study, if needed. The apheresis schedule is not allowed to change during the double-blind period of the trial and must permit that an apheresis coincides with each study visit

- 9. Estimated glomerular filtration rate (eGFR) >30 mL/min/1.73 m² at screening
- 10. Willing to follow all study procedures including adherence to study visits, fasting blood draws, and compliance with study treatment regimens

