8.3.1 LDL-cholesterol

The primary efficacy assessment will be LDL-C. Samples for LDL-C will be collected at screening and on Days 1, 90, 150, 270, 330, 360, 450, 510, 630 and 720 (Table 8-1).

After randomization (Day 1) until the Day 360 visit, the results from the LDL-C laboratory assessments must be blinded to participants, investigator staff, persons performing the assessments, and the CTT.

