2.1.1 General definitions

Study day

Study day will be defined as the number of days since the date of first dose of double-blind treatment. The date of first dose of double-blind treatment will be defined as Day 1 and the day before the first dose of study drug will be defined as Day -1.

Novartis	For business use only	Page 18
SAP amendment 4		CKJX839C12301

Therefore, for a particular date, study day will be calculated as follows:

For dates on or after the first date of double-blind treatment,

Study day = Assessment date – Date of first dose of double-blind treatment + 1;

For dates prior to the first date of double-blind treatment,

Study day = Assessment date – Date of first dose of double-blind treatment.

In case, participant has been randomized but has not received double-blind treatment then randomization visit day will be considered as Day 1.

Baseline definition

In general, for both Part 1 and Part 2, baseline value is defined as the last measurement collected on or prior to the first dose of double-blind treatment.

Post-baseline measurement

Post-baseline values are defined as those measurements that were collected after the first dose of double-blind treatment.

When change from baseline is of interest the following formula will be used for each scheduled visit and time-point where baseline and post-baseline values are both available:

Absolute change from baseline = post-baseline value – baseline value.

Percent change from baseline = (post-baseline value - baseline value) / baseline value*100.

Reflexive LDL-C

The endpoints involving LDL-C will use a reflexive LDL-C approach. The calculated LDL-C will be utilized unless triglycerides are greater than 400 mg/dL and/or calculated LDL-C is less than 40 mg/dL, in which case beta quantification LDL-C (i.e., LDL_C directly measured by ultracentrifugation) will be additionally performed and used for the analysis.

VLDL-C

The endpoints involving VLDL-C will follow the same approach as reflexive LDL-C.

Re-derivation of age-strata for mis-stratified participants

If any subject will be mis-stratified for age-group during randomization, collected age of that participant will be used to re-derive the correct age-strata at analysis level and will be used for all analyses, as needed.

Discontinuation visit mapping

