2.8.4 Diabetes assessment

Diabetes will be assessed by the analysis of:

- TEAEs,
- Change in glucose-related laboratory values over time,
- Shifts from baseline in glucose control category and,
- Incidence of post-baseline new onset of diabetes.

Note that diabetes related tables dealing with the fasting plasma glucose parameter will require the lab sample to be taken fasting. Samples taken while the subject was not fasted will not be analyzed.

Unless otherwise specified, baseline of fasting plasma glucose will be defined as the average of Screening and Day 1 assessments. If one fasting plasma glucose value is missing (Screening or Day 1), the baseline will be based on the available data. For HbA1c, the Day 1 assessment will be considered as baseline. If missing, then the baseline will be based on the assessment at screening.

Diabetes TEAE

Novartis	Confidential	Page 33 of 48
Clinical Study Report Appendix 16.1.9, v1.0		Study No. CKJX839C12301

Novartis	For business use only	Page 32
SAP amendment 4		CKJX839C12301

New onset/worsening of diabetes will be identified by the search criteria specified in Appendix 5.4. The analysis will be performed for all subjects and then by baseline diabetes status. A participant will be identified as being diabetic at baseline if the medical history notes that the subject is diabetic or the baseline HbA_{1c} value is $\geq 6.5\%$ or the baseline fasting plasma glucose is ≥ 126 mg/dL. This summary will be provided by treatment and Part.

Change in Glucose-related Laboratory Values over Time

This analysis only utilizes laboratory data (fasting plasma glucose and HbA_{1c}). The change from baseline to the last on-treatment observation and the worst on-treatment observation will be summarized by treatment and Part, separately for fasting plasma glucose and HbA_{1c} for all participants and then by baseline glucose control status. Baseline glucose control status will be identified separately for fasting plasma glucose and HbA_{1c} using the values provided in the table below (note that medical history will not be considered for this analysis). Figures will also be created showing change in mean fasting plasma glucose and HbA_{1c} values over time by baseline glucose control status.

Parameter	Baseline Glucose Control Status (Laboratory Values)
Fasting Plasma Glucose	<100 mg/dL
	\geq 100 to <126 mg/dL
	≥126 mg/dL
HbA1c	<5.7%
	\geq 5.7 to < 6.5%
	≥6.5%

Shifts from Baseline in Glucose Control Category

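### The LDL-C models leave out the screening LDL-C, a second pre-randomization value on the same therapy; adding it would reduce variance by about 0-11% without changing the estimand.

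*SAP*

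**What the plan says.** **Model.** SAP 2.5.2 sets out the primary ANCOVA: "The model will include the fixed effects of treatment group and baseline age group". The same sentence adds baseline LDL-C as the one continuous covariate, and each arm has its own residual variance. Protocol 12.4.2 lists the same terms.

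**Baseline.** Under SAP 2.1.1 the "baseline value is defined as the last measurement collected on or prior to the first dose of double-blind treatment". That single value is both the denominator of the percent change and the LDL-C covariate.

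**Data collected.** Protocol 8.3.1: "Samples for LDL-C will be collected at screening and on Days 1, 90, 150, 270, 330, 360, 450, 510, 630 and 720". Inclusion criterion 4 (Protocol 5.1) requires "Fasting LDL-C >130 mg/dL (3.4 mmol/L) at the screening visit, measured at the central laboratory", so every eligible participant has this value. Protocol Section 3 (Study design) says that eligible participants are "required to maintain their current lipid-lowering treatment unchanged for Part 1 (Year 1) of the study (including the screening/run-in period", and inclusion criterion 7 asks for a stable dose for at least 30 days before screening.

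**Where screening LDL-C is used.** It decides eligibility, and under the baseline definition it would stand in if Day 1 were missing. It is not a term in the primary model (SAP 2.5.2), the sensitivity models (2.5.5), the key secondary models (2.6.2) or the imputation models (5.7.1, 5.7.2). For glucose, SAP 2.8.4 does combine the two visits: "baseline of fasting plasma glucose will be defined as the average of Screening and Day 1 assessments".

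**The concern.** Screening and Day 1 LDL-C are two readings of the same quantity, about four weeks apart, on the same background therapy and both before randomization. Biological and assay noise in the Day 1 value enters the endpoint through the denominator. Adjusting for that same noisy value removes only part of it; a second reading can remove more.

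The washout imputation has the same gap. For inclisiran participants without a Day 330 value, Steps 3 and 4 of SAP 5.7.1 predict from baseline, age group and Day 330 data alone, so one LDL-C reading carries the individual prediction.

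At stake is the width of the confidence intervals for the LDL-C endpoints: the primary endpoint and the first two key secondary endpoints. The validity of the comparison is not at stake.

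**Working it through.** **1. The plan's own figure.** The minimum is 102 participants at 2:1 (68 inclisiran, 34 placebo), one-sided 0.025; 141 were enrolled (SAP 1.1), that is 94 and 47 at exactly 2:1. The assumed effect, SDs and power are blacked out, so 102 cannot be reproduced. What it can detect follows from (z_alpha + z_power) x sqrt(1/34 + 1/68), where the square root is 0.210:

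- 80% power: (1.960 + 0.842) x 0.210 = 0.59 SD
- 90% power: (1.960 + 1.282) x 0.210 = 0.68 SD
- 99% power: (1.960 + 2.326) x 0.210 = 0.90 SD

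With an assumed SD of 30 points, power at 102 is 88.8% for a 20-point difference, 99.7% for 30 points and above 99.9% for 40 points. With an assumed SD of 40 the figures are 66.3%, 94.6% and 99.7%.

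**2. Closed form, LDL-C on an additive scale.** Let a = corr(screening, Day 1), b = corr(Day 1, Day 330), c = corr(screening, Day 330). With both covariates R² = (b² + c² - 2abc)/(1 - a²), and the residual variance relative to Day 1 alone is (1 - R²)/(1 - b²). None of the correlations is in the documents.

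- All equal to r: the ratio is (1 + 2r)/(1 + r)², giving 0.89 at r = 0.5, 0.83 at 0.7 and 0.78 at 0.9.
- a = 0.8, b = c = 0.7: R² = (0.98 - 0.784)/0.36 = 0.544, ratio 0.456/0.51 = 0.89.
- a = 0.9, b = c = 0.6: ratio 0.97.
- Pure serial decay, c = ab: R² = b², ratio 1.00, no gain.

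**3. Simulation of the actual endpoint.** Percent change from Day 1, 2:1, screening LDL-C above 130 mg/dL, arm-specific residual variances, complete data, 3,000 trials per row. Assumed: median LDL-C 185 mg/dL, between-person SD of log LDL-C 0.25, mean reduction 35%. The variance ratio is with versus without screening LDL-C.

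| Visit CV / long-term drift / response SD | Ratio, N=102 | Ratio, N=141 | Mean SE, N=102 (points) |
|---|---|---|---|
| 10% / 10% / 15 | 0.927 | 0.916 | 3.78 to 3.64 |
| 15% / 10% / 15 | 0.933 | 0.932 | 4.80 to 4.62 |
| 15% / 10% / 20 | 0.927 | 0.939 | 5.09 to 4.92 |
| 10% / 15% / 20 | 0.958 | 0.952 | 4.71 to 4.60 |
| 8% / 15% / 20 | 0.974 | 0.963 | 4.41 to 4.34 |
| 15% / 5% / 10 | 0.893 | 0.914 | 4.21 to 4.00 |
| Serial decay, no visit noise (15% drift at each step, response SD 15) | 1.016 | 1.009 | 3.46 to 3.48 |

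The mean estimate moved by at most 0.03 points. The N columns differ by up to 0.021 in no consistent direction, which indicates the simulation error. The simulated screening-Day 1 correlation was 0.67 to 0.88.

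**4. How much visit noise restores the gain.** Further runs at 94 versus 47 combined a serially decaying component (log-SD 0.10) with independent visit noise. Variance ratios were 1.01 at 0% noise, 0.99 at 3%, 0.96 at 5% and 0.92 to 0.95 at 8-12%.

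**5. In participants and interval width.** At 102, a ratio of 0.974 is worth 102 x (1/0.974 - 1) = 2.7 participants; 0.893 is worth 102 x (1/0.893 - 1) = 12.2. The largest SE reduction is 1 - sqrt(0.893) = 5.5%. For the second row, the 95% half-width shrinks by 1.96 x (4.80 - 4.62) = 0.35 points.

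**The case against.** Five arguments on the other side deserve weight.

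- **No error.** Treatment, the stratification factor and baseline LDL-C make a valid ANCOVA that agrees with the protocol. This stands.
- **The gain is assumed, and serial decay could turn it into a loss.** A reader might infer that the plan demonstrably loses precision. The documents do not show that: they give no within-person correlations. Screening is about a year before Day 330, so some decay is plausible. But the loss appears only when independent visit noise is close to zero, and it is then 1-2%.
- **No test result would plausibly change.** The adult trials showed placebo-adjusted reductions of 48-52% (Protocol 1.1), and power is high over most of the range above. This stands; the benefit is a slightly narrower interval.
- **It is not free.** A reader might infer that the precision can be recovered at no cost. No new samples are needed, but protocol text and two imputation algorithms change, and one degree of freedom is spent. Apo B, Lp(a), non-HDL-C and total cholesterol have no scheduled screening value (Protocol Table 8-1), so the adjustment sets in the testing hierarchy would differ. This stands as a real but small cost.
- **Day 1 has its own rationale.** Protocol 4.1 gives stabilization of background therapy as one purpose of the run-in. That supports Day 1 as the denominator; it does not make screening LDL-C uninformative as a covariate.

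The glucose rule in SAP 2.8.4 might be read as an inconsistency. It is not one: it defines a baseline for diabetes summaries, and the same section uses Day 1 alone for HbA1c. Nor is Day 1 LDL-C the only adjustment, since age group is in the model.

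**Conclusion.** The point holds as an efficiency improvement. A second pre-randomization LDL-C, collected for eligibility on unchanged therapy, is unused in every LDL-C analysis and imputation model. Because it precedes randomization, adjusting for it does not change the estimand or bias the comparison, and the entry cut-off of 130 mg/dL does not spoil it as a covariate.

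The size is a variance reduction of about 0-11% (standard error about 0-6% smaller), with a possible loss of about 1-2% if there is almost no independent visit noise. This rests on the assumed variances, correlations and effect above and on complete-data simulations. The larger closed-form reductions, up to 22%, should not be claimed for percent change, where variation in response and the Day 1 denominator remain.

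Nothing here suggests that the primary analysis is invalid or underpowered.

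**What to change.** Before Part 1 unblinding:

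- Add screening LDL-C as a second continuous covariate in the LDL-C ANCOVA and MMRM models (SAP 2.5.2, 2.5.5, 2.6.2), with the same change in Protocol 12.4.2 and 12.4.5.
- Add it to the LDL-C imputation models (SAP 5.7.1, 5.7.2), including Steps 3 and 4 of the washout model, so that they contain every term of the analysis model.
- Keep Day 1 as the denominator, so the endpoint is unchanged.
- State the rule for anyone without a Day 1 value, for whom baseline and screening would be the same number.
- State that the other lipid models keep a single baseline because no screening value is scheduled.

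The cost is SAP and protocol wording, reprogramming of the imputation, one degree of freedom and an adjustment set that differs between LDL-C and the other lipids. No new data are needed.

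Timing limits this for the present trial. The statistical-methods appendix that carries the SAP already records an analysis added after the Part 1 lock, and Protocol 6.4 has the trial team unblinded after that lock. From then on the adjusted analysis should be reported only as a labelled supplementary analysis beside the unchanged primary result.
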